6.1.3.2 Dosing with single capsule (140 μg) tropifexor supply

After tropifexor and matching placebo is replaced by the 140 μ g hard gelatin single capsule, in order to maintain the blind, placebo capsules matching tropifexor 140 μ g and placebo tablets matching licogliflozin (LIK066) 10 mg will be given to participants as indicated in Table 6-6, so that all participants will receive 1 capsule and 3 tablets per day. **One capsule from the bottle**, and **3 tablets from the blister pack** should be taken close to the evening meal; either just prior to (within 5 minutes) consuming the evening meal, or no more than 30 minutes after consuming the evening meal and at about the same time each day.

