6.7.2 Instruction for prescribing and taking study treatment

Participants should be instructed to take the dose of study medication daily, close to the evening meal; either just prior to (within 5 minutes) consuming the evening meal, or no more than 30 minutes after consuming the evening meal and at about the same time each day. Only at Baseline and week 4 visit, the participants should take their doses at the clinic following a meal instead of in the evening.

Once the protocol amendment v02 is approved and after the tropifexor (LJN452) 10, 30 and 100 μ g and matching placebo hard gelatin capsule supply is depleted, the participant will receive 9 blister packs in a box (10 mg licogliflozin or matching placebo tablets) and 1 bottle of 140 μ g hard gelatin capsules (replacing the 10, 30 and 100 μ g tropifexor or matching placebo capsules) for each 4 week period every 4 weeks through Week 20. At the Week 24, Week 32 and Week 40 visits 2 sets of 4 week supplies of study medication will be distributed to accommodate the 8 weekly visit schedule (Table 8-1). The participants will take **3 tablets** from the blister pack and **1 capsule** from the bottle daily as described above.

If the COVID-19 or other pandemic prevents on-site visits the site may arrange delivery of study medication to a participant's home.

Novartis Amended Protocol Version 02 (Clean) Confidential

6.7.2.1 Overview of treatment - type and number of capsules and tablets taken per day

The 140 μ g dose of tropifexor and its matching placebo are each available as a single hard gelatin capsule. Participants on the study at the time of availability of the single tropifexor/placebo capsule, may continue on the 3-capsule tropifexor (100 μ g + 30 μ g + 10 μ g) or matching placebo regimen, as shown in Table 6-5, until the available 3 capsule supply is depleted.

	·····				······································			
Treatme nt Arm	Tropifexor (LJN452) 10µg capsu le	Tropifexor (LJN452) 30µg capsu le	Tropifexor (LJN452) 100µg capsule	Tropifexor (LJN452) Placebo capsule	Licogliflozi n (LIK066) 10mg table t	Licogliflozi n (LIK066) Placebo tablet	Frequency	
Arm A	1	1	1	0	3	0	Daily	
Combo Tropifexor (L JN452) 140 µg								
& Licogliflozin (LIK066)								
30 mg								
Arm B	1	1	1	0	0	3	Daily	
Mono Tropifexor (L JN452) 140 µg								
Arm C	0	0	0	3	3	0	Daily	
Mono Licogliflozin (LIK066) 30 mg								
Arm D	0	0	0	3	0	3	Daily	
Placebo								

Table 6-5Dosing with 3 capsule (10 + 30 + 100 µg) tropifexor supply

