
After the 3-capsule supply is depleted, participants will take 1-capsule of 140 µg tropifexor or matching placebo daily as described in Table 6-6. No change is made to licogliflozin dosing.

Novartis Amended Protocol Version 02 (Clean) Confidential

Table 6-6	Dosing with single capsule (140 μg) tropifexor supply						
Treatment Arm	Tropifexor (LJN452) 140µg capsule	Tropifexor (LJN452) Placebo capsul e	Licogliflozin (LIK066) 10mg tablet	Licogliflozin (LIK066) Placebo tablet	Frequency		
Arm A Combo Tropifexor (LJN45 2) 140 μg & Licogliflozin (LIK06 6) 30 mg	1	0	3	0	Daily		
Arm B Mono Tropifexor (LJN45 2) 140 μg	1	0	0	3	Daily		
Arm C Mono Licogliflozin (LIK06 6) 30 mg	0	3	3	0	Daily		
Arm D Placebo	0	3	0	3	Daily		

IMPORTANT: Please ensure that the date of the change, and the number of capsules (from 3 capsule to 1 capsule) is accurately captured in the eCRF Change in Dosing log for each participant.

Dosing recommendations:

1. Participants should take 3 Tablets from the blister pack (licogliflozin or matching placebo) & 1 or 3 Capsules (tropifexor or matching placebo) depending on current supply close to the evening meal; either just prior to (within 5 minutes) consuming the evening meal, or no more than 30 minutes after consuming the evening meal, at about the same time each day. Participants directed to take 3 capsules must be reminded that one capsule is to be taken from each of the 3 tropifexor/placebo bottles provided. At Baseline and week 4 the dose will be taken in the morning at the clinic close to a meal instead of in the evening.

Confidential

- 4. Participants should be instructed to swallow the capsules and tablets whole and not to chew them.
- 5. If vomiting or diarrhea occurs during the course of treatment, no re-dosing of the participant is allowed before the next scheduled dose.
- 6. If a dose is missed and not remembered the same day, it should not be made up on a subsequent day.

All kits of study treatment assigned by the IRT will be recorded/databased in the IRT system.

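### Table 6-6 lists 3 placebo capsules a day for Arms C and D, although the text gives every participant 1 capsule a day on the single-capsule supply

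*Protocol*

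**What the plan says.** Protocol Section 6.1.3.2 describes dosing on the single-capsule supply. It points to Table 6-6 for how placebo is allotted and states the result: "so that all participants will receive 1 capsule and 3 tablets per day".

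Table 6-6 has four count columns: active capsule, placebo capsule, active tablet and placebo tablet. Its last two rows read "Arm C Mono Licogliflozin (LIK06 6) 30 mg 0 3 3 0 Daily" and "Arm D Placebo 0 3 0 3 Daily". Both therefore give 3 placebo capsules a day. Arms A and B have 1 active capsule and no placebo capsule.

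Other current text on the same supply:

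- Sections 6.1.1 and 6.1.3: one 140 µg capsule, tropifexor or matching placebo, each day.
- Section 6.7.2, for each 4-week period: "the participant will receive 9 blister packs in a box (10 mg licogliflozin or matching placebo tablets) and 1 bottle of" the 140 µg capsules, with one capsule a day from that bottle and no distinction by arm.
- Section 6.7.2.1, lead-in to Table 6-6: "participants will take 1-capsule of" the 140 µg strength or its placebo.
- Note directly under Table 6-6: sites must ensure that "the number of capsules (from 3 capsule to 1 capsule) is accurately captured in the eCRF Change in Dosing log for each participant".
- Dosing recommendation 1: "1 or 3 Capsules (tropifexor or matching placebo) depending on current supply".

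Table 6-5 covers the earlier three-capsule supply. Its Arm D row is "Arm D 0 0 0 3 0 3 Daily", which also shows 3 placebo capsules.

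**The concern.** Section 6.1.3.2 names Table 6-6 as the means by which everyone takes 1 capsule, and the table fails to do this in two of the four arms. Both statements are current protocol text, so this is not a leftover from the amendment log.

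What is at stake is the blind. The trial uses a double dummy because the two products look different, and Section 6.4 requires each placebo to match its active counterpart, including in how it is scheduled. If Table 6-6 were carried out literally, a participant on 1 capsule would be in an arm with tropifexor (A or B) and a participant on 3 would be in an arm without it (C or D). Anyone using the table to specify IRT text, labels, kit quantities or drug accountability would build in that difference.

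**Working it through.** No sample-size, power or alpha formula applies. The check is a row sum of the counts in each table, compared with the text.

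**Three-capsule supply (Table 6-5).** The columns are active 10, 30 and 100 µg capsules, placebo capsule, active tablet and placebo tablet. Section 6.1.3.1 gives 3 capsules and 3 tablets to everyone.

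| Arm | Capsules | Tablets | Total |
|---|---|---|---|
| A | 1+1+1+0 = 3 | 3+0 = 3 | 6 |
| B | 1+1+1+0 = 3 | 0+3 = 3 | 6 |
| C | 0+0+0+3 = 3 | 3+0 = 3 | 6 |
| D | 0+0+0+3 = 3 | 0+3 = 3 | 6 |

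The statement in the text is reproduced in all four arms.

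**Single-capsule supply (Table 6-6).** Section 6.1.3.2 gives 1 capsule and 3 tablets, which is 4 units, to everyone.

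| Arm | Capsules | Tablets | Total | Text |
|---|---|---|---|---|
| A | 1+0 = 1 | 3+0 = 3 | 4 | 4 |
| B | 1+0 = 1 | 0+3 = 3 | 4 | 4 |
| C | 0+3 = 3 | 3+0 = 3 | 6 | 4 |
| D | 0+3 = 3 | 0+3 = 3 | 6 | 4 |

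The statement is reproduced for Arms A and B only. The tablet counts are right throughout, so the error is confined to the placebo-capsule cells of Arms C and D.

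**Is it an extraction fault?** No. Each Table 6-6 row carries four counts for four count columns, and the rows for Arms A and B make sense in that alignment.

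**Where the 3 probably comes from.** It equals the placebo-capsule entry for the same arms in Table 6-5. There it is correct, because the active arms take 1+1+1 capsules. Carry-over is an inference, but no other explanation is apparent.

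**Supply.** Over 28 days Table 6-6 implies 1 × 28 = 28 capsules in Arms A and B and 3 × 28 = 84 in Arms C and D. Section 6.7.2 issues one bottle to each participant for the same period. The number of capsules per bottle is not stated.

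**Participants in the affected arms.** 80 + 80 = 160 of 380 planned. This is an upper limit, since some may finish on the three-capsule supply.

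**After correction.** With 1 in place of 3 in the two cells, every arm has 1 + 3 = 4 units a day, as Sections 6.1.3.2 and 6.7.2 state.

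**The case against.** The case for treating this as purely editorial has real substance. The right dose appears many times around the table. Participants and site staff are blinded at allocation and dosing (Table 6-4), and sites choose packages by IRT medication number (Section 6.7), so no one at a site can apply a row specific to an arm. What sites act on is the arm-neutral text, and that is correct. The surplus capsules would be placebo, so no one would be overdosed with active drug. No IRT specification or label is available to show that the table was ever used. On Section 6.4, Table 6-6 lists daily dosing in all four arms, and it can be argued that units per dose are not part of the schedule.

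Most of this stands, and it limits the consequence. No unblinding or wrong dose is shown, and the 160 and the 28 against 84 describe what the table says, not what happened. It does not make the table harmless. Blinded sites cannot use the arm rows, but whoever specifies kits, labels or IRT text can, and Section 6.1.3.2 sends that reader to Table 6-6 for the placebo allotment. The Section 6.4 point adds little: whether or not count belongs to schedule, a capsule count that differs by arm defeats the purpose of the double dummy.

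**Conclusion.** The inconsistency is real and should be fixed. Table 6-6 is wrong in two cells: it gives Arms C and D 3 capsules and 6 units a day, where the text gives 1 capsule and 4 units in every arm. That the table is at fault, and not the text, rests on the agreement of every other statement about the single-capsule supply and on the one-bottle dispensing rule.

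The effect on the trial is conditional. The blind would be at risk only if labels, kits or IRT text had been built from the table, and the documents do not show this. Estimands, sample size, power and alpha are not affected.

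**What to change.** In Table 6-6, change the placebo-capsule entries for Arms C and D from 3 to 1. Then confirm that the IRT and label text for the single-capsule supply follow Section 6.1.3.2.

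As a wording clean-up, limit the sentence in Section 6.7.2.1 that tells participants the bottles differ in content, and to take one capsule from each, to the three-capsule supply. It presupposes several bottles; it does not change the dose.

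The cost is two table cells, one sentence and a document check. Sites need a clarification only if that check finds a mismatch.

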6.1.4 Treatment duration

The planned duration of treatment is 48 weeks. Participants may be discontinued from treatment earlier due to unacceptable tolerability, disease progression and/or at the discretion of the investigator or the participant.

Novartis	Confidential	Page 78 of 160
Amended Protocol Version 02 (Clean)		Protocol No. CLJN452D12201C
If discontinuation of study treatment	occurs, the participant	should NOT be considered
withdrawn from the study. The participation	ant should return to the c	clinic as soon as possible, after
discontinuation of study drug. In this	case, if the participant	and study investigator agree,
participant may continue in the study w	vithout treatment.	
	Alternatively, a study	treatment discontinuation visit

will be conducted.

6.2 Other treatment(s)

No other treatment beyond investigational drug and control drug are included in this trial.

An overview of the prohibited medication is given in Table 6-3, and the summary of permitted medication if on stable dose is in Table 6-2.

6.2.1 Concomitant therapy

The investigator must instruct the participant to notify the study site about any new medications he/she takes after the participant is enrolled into the study.

All medications, vaccines, procedures, and significant non-drug therapies (including physical therapy and blood transfusions) administered after the participant was enrolled into the study must be recorded on the appropriate case report forms (CRF).

Each concomitant drug must be individually assessed against all exclusion criteria/prohibited medication. If in doubt, the investigator should contact the Novartis medical monitor before randomizing a participant or allowing a new medication to be started. If the participant is already enrolled, contact Novartis to determine if the participant should continue participation in the study. There are no restrictions related to COVID-19 vaccines, and these are allowed throughout study participation as permitted by local regulations.

Drugs to control medically significant lipid abnormalities (which have been confirmed upon repeat testing) can be prescribed according to local standard of care. Participants on medications specified in Table 6-2 can be included if these medications are medically necessary, and the investigator feels the dose will remain stable for the duration of the double-blind treatment period. In addition, doses of oral anti-diabetic medication, insulin, GLP-1 agonists, thyroid hormone, and estrogen or estrogen containing birth control, must be stable for at least 3 months prior to the Baseline visit. Sliding scale insulin therapy is allowed if this approach has been implemented for at least 3 months prior to the Baseline visit. Insulin dose adjustment is permitted during the study if required. Doses of vitamin $E \leq 800$ IU/day must be stable for at least 6 months prior to the Baseline visit. A stable dose is defined as a dose within 25% of the Baseline dose. New use or dose adjustments > 25% of the Baseline dose of these medications is not allowed after entering the study.

Table 6-2	Medications permitted only if dose is stable (within 25 percent of
	Baseline dose) and expected to remain stable through the double-
	blind treatment period

Medication	Stable dose start
Oral anti-diabetic medications	At least 3 months prior to the Baseline visit
Insulin	At least 3 months prior to the Baseline visit
GLP-1 agonists such as liraglutide, exenatide, lixisenatide, albiglutide or dulaglutide	At least 3 months prior to the Baseline visit
Beta-blockers and thiazide diuretics	At or before Screening Visit 1
Vitamin E < 800 IU/day	At least 6 months prior to the Baseline visit
Thyroid hormone	At least 3 months prior to the Baseline visit
Phenothiazines	At or before Screening Visit 1
Estrogen or estrogen containing birth control	At least 3 months prior to the Baseline visit

6.2.2 **Prohibited medication**

Use of the treatments displayed in the below Table 6-3 is NOT allowed after the start of investigational drug, and should be discontinued as soon as screening is considered so that participants medications and conditions are stable and the screening assessments reflect the participant's Baseline condition.

Alcohol consumption is to be strongly discouraged, and if consumed should not exceed 20 g/day (14 units/week) in females and 30 g/day (21 units/week) in males. A "unit" of alcohol is equivalent to 12-ounce, 355 ml beer, 4-ounce, 120 ml glass of wine, or 1 ounce, 30 ml shot of hard liquor.

Use of methotrexate is prohibited as liver fibrosis has been reported with its chronic use.

A study in healthy volunteers was conducted to investigate the effect of UDP glucuronosyltransferase (UGT) inhibition on the pharmacokinetics (PK) of tropifexor by coadministration with the UGT1A1 inhibitor, atazanavir (ATZ) (CLJN452A2110). The inhibition of UGT1A1 by ATZ did not lead to increased exposure of tropifexor, suggesting that inhibition of the UGT1A1 pathway has no clinically relevant impact on tropifexor PK. Therefore, no Drug-Drug Interactions are expected between tropifexor and UGT1A1 inhibitors based on UGT1A1 activity / genotype, and therefore use of these compounds is not prohibited in this study. Non-selective UGT inhibitors are prohibited.

Medication	Timing
SGLT2 Inhibitors or combined SGLT1/2 inhibitors	Stop at least 3 months prior to Baseline
Such as: canagliflozin, dapagliflozin, empagliflozin	
Pharmacologically active weight-loss medications	Stop at least 3 months prior to Baseline
Such as: lorcaserin, phentermine/topiramate, bupropion-naltrexone HCL, orlistat)	
Treatment with drugs that have a high incidence of diarrhea	Stop at or before Screening Visit 1
Such as: Orlistat, Acarbose.	
Treatment with drugs that alter intestinal motility	Stop at or before Screening Visit 1
Such as: e.g. erythromycin, metoclopramide, tegaserod, methylnaltrexone, alvimopan, loperamide, diphenoxylate and atropine (Lomotil) and difenoxin and atropine (Motofen))	
Non-selective UGT inhibitors:	Stop at or before Baseline
Such as: diclofenac, probenecid, valproic acid	
Strong CYP3A4 inhibitors:	Stop at or before Baseline
Such as: viekira Pak, indinavir/ritonavir, tipranavir/ritonavir, ritonavir, cobicistat (GS- 9350) ,indinavir, ketoconazole, troleandomycin, telaprevir, danoprevir/ritonavir, elvitegravir/ritonavir, saquinavir/ritonavir, lopinavir/ritonavir, itraconazole, voriconazole,mibefradil, LCL161, clarithromycin, posaconazole, telithromycin, grapefruit juice, conivaptan, nefazodone, nelfinavir, saquinavir, idelalisib, boceprevir, darunavir/ritonavir.	
Strong CYP3A4 inducers:	Stop at or before Baseline
Such as: avasimibe, carbamazepine, phenytoin, rifampin, St. John's wort (Hypericum perforatum), rifabutin, phenobarbital, mitotane, enzalutamide.	
Methotrexate	Stop at least 3 months prior to Baseline
Vitamin E doses > 800 IU/day	Stop (or reduce dose) at least 6 months prior to Baseline
Drugs approved in any market for treatment of NASH	Stop at least 6 months prior to Baseline
Alternative Liver Protection medication:	Stop at or before Screening Visit 1
Silymarin; Bicyclol; Polyene Phosphatidylcholine (Essentiale); Diammonium Glycyrrhizinate; Reduced glutathione (GSH); S- adenosylmethionine–methionine; Ursodeoxycholic Acid (UDCA)	

Table 6-3Prohibited medications

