2.1 Primary estimands

The primary question of interest to be answered in the trial using liver histology is:

Does the combination therapy (tropifexor + licogliflozin), administered once per day in participants with NASH and stage 2 or 3 fibrosis over 48 weeks, lead to histologic improvement compared with placebo treatment?

This question gives rise to 2 primary estimands, due to 2 different endpoints of interest.

The first primary estimand has the following attributes with respect to the primary question:

- Treatment: The randomized treatment (the investigational combination therapy <tropifexor 140 μ g + licogliflozin 30 mg> or the placebo) taken for 48 weeks, irrespective of administration or dose changes in anti-diabetic and lipid-lowering concomitant medication according to medical need. More details about the treatment are provided in Section 6
- Population: Participants with NASH (using NAFLD Activity Score (NAS) ≥ 4 with at least 1 point each in inflammation and ballooning on the screening histology assessment performed by the central reader) and stage 2 or 3 fibrosis (using NASH CRN fibrosis criteria), as defined by the inclusion and exclusion criteria of the study Section 5.
- Endpoint: Whether the participant achieves at least one stage improvement in fibrosis without worsening of NASH at Week 48 compared with Baseline.
- Summary measure: Odds ratio of the participants achieving at least one stage improvement in fibrosis without worsening of NASH, at Week 48 compared with Baseline, of the two treatments for each pairwise comparison.

The second primary estimand has the subsequent characteristics with respect to the primary question:

- Treatment: The randomized treatment (the investigational combination therapy <tropifexor 140 μ g + licogliflozin 30 mg> or the placebo) taken for 48 weeks, irrespective of administration or dose changes in anti-diabetic and lipid-lowering concomitant medication according to medical need.
- Population: Participants with NASH and stage 2 or 3 fibrosis confirmed by biopsy, as defined by the inclusion and exclusion criteria of the study.

Novartis	Confidential	
Amended Protocol Version 02 (Clean)		I

- Endpoint: Whether the participant has resolution of NASH and no worsening of fibrosis at Week 48 compared with Baseline.
- Summary measure: Odds ratio of the participants obtaining resolution of NASH and no worsening of fibrosis, at Week 48 compared with Baseline, of the two treatments for each pairwise comparison.

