10.2.3.5 Hypoglycemia

Participants with T2DM treated with antidiabetic medications (especially insulin and sulfonylureas) are at risk of hypoglycemia. Licogliflozin is effective in reducing glucose level and may lead to hypoglycemia in participants receiving other antidiabetic medications (especially insulin and insulin secretagogue). Diabetic participants must continue their routine self-monitoring of glucose levels and be educated regarding hypoglycemic symptoms (dizziness, lightheadedness; palpitations, heart racing/pounding, shaking, sweating, hunger, blurred vision, impairment of motor function, confusion), explanation of possible triggers (strenuous exercise, delayed meals, changes in meal composition, illness, periods of prolonged fasting) and treatment by the physician managing the participant's diabetes.

Novartis	Confidential	Page 129 of 160
Amended Protocol Version 02 (Clean)		Protocol No. CLJN452D12201C
		44 4 44 4

During the course of the study, if a participant experiences clinically symptomatic hypoglycemia, an immediate medical evaluation should be conducted. Glucose levels will be measured. If a confirmed glucose level is <56 mg/dL by repeated measurement, background anti-diabetic medication may require dose adjustment, or study treatment may be interrupted and the participant treated according to standard of care for hypoglycemia.

Events consistent with or suspected to be hypoglycemia, should be recorded in the participant diary and on the AE eCRF.

Furthermore, this study outlines inclusion and exclusion criteria to minimize this risk and exclude participants at risk of this adverse event (please refer to Section 5 for details).

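### The post-entry limit on anti-diabetic medication in Section 6.2.1 contradicts itself on insulin, does not fit the primary estimands' treatment definition, is not reconciled with the hypoglycemia section, and leaves the handling of such changes in the primary analysis unclear

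*Protocol*

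**What the plan says.** **Protocol 6.2.1 and Table 6-2.** For entry, "doses of oral anti-diabetic medication, insulin, GLP-1 agonists, thyroid hormone, and estrogen or estrogen containing birth control, must be stable" for at least 3 months before Baseline, and "A stable dose is defined as a dose within 25% of the Baseline dose". After entry: "New use or dose adjustments > 25% of the Baseline dose of these medications is not allowed after entering the study". Table 6-2 lists oral anti-diabetics, insulin and GLP-1 agonists as permitted only while the dose stays within 25% of Baseline through the double-blind period. The same paragraph of 6.2.1 also states "Insulin dose adjustment is permitted during the study if required". Lipid drugs are treated differently: "Drugs to control medically significant lipid abnormalities (which have been confirmed upon repeat testing) can be prescribed according to local standard of care".

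**Protocol 10.2.3.5 (Hypoglycemia).** Hypoglycemia is an adverse event of special interest, and insulin and insulin secretagogues are singled out as the background drugs of concern. If a glucose below 56 mg/dL is confirmed, "background anti-diabetic medication may require dose adjustment, or study treatment may be interrupted", with treatment according to standard of care. No size limit is given and 6.2.1 is not mentioned.

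**Protocol 2.1.** Both primary estimands take the randomized treatment "irrespective of administration or dose changes in anti-diabetic and lipid-lowering concomitant medication according to medical need".

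**Protocol 2.1 and 12.4.3, intercurrent event 3.** Addition or removal of a potentially confounding medication is handled by treatment policy, with a hypothetical strategy in a supplementary analysis. Section 12.4 lists initiation of another T2DM medication among the intercurrent events.

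**Protocol 12.4.4.** Any primary endpoint after an intercurrent event is imputed by multiple imputation under missing at random.

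**The concern.** Three parts of the protocol govern the same act, a change in background anti-diabetic therapy during the study, and they do not agree. The concomitant-therapy section restricts it. The safety section offers it as one response to a named event of special interest. The estimand section builds it into the treatment being evaluated.

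Two things are at stake. Sites have conflicting instructions, most plainly for insulin, so the same action could be recorded as ordinary conduct at one site and as a protocol deviation at another. Analysts also cannot tell whether a Week 48 biopsy taken after such a change is to be used as observed or replaced by an imputed value. That choice decides which estimand the primary analysis targets.

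**Working it through.** The point is one of consistency. The only figures involved are the 25% limit (6.2.1) and the 56 mg/dL trigger (10.2.3.5). Both are set by rule, so there is nothing to recompute.

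**Step 1: possible changes against each rule.** A change is measured as |new dose − Baseline dose| / Baseline dose. Stopping a drug gives |0 − D| / D = 100%, which exceeds 25%. Any agent not taken at entry is new use.

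| Change after entry | 6.2.1 and Table 6-2 | 10.2.3.5 | Treatment attribute in 2.1 |
|---|---|---|---|
| Insulin, more than 25% | Permitted by one sentence, forbidden by another and by Table 6-2 | Within the adjustment provided for | Part of treatment if for medical need |
| Oral anti-diabetic or GLP-1 agonist, 25% or less | Allowed | Within the adjustment provided for | Part of treatment if for medical need |
| Oral anti-diabetic or GLP-1 agonist, more than 25% | Forbidden | Within the adjustment provided for, since no size limit is set | Part of treatment if for medical need |
| New anti-diabetic agent | Forbidden | Not called for | Part of treatment if for medical need |

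The first row is a contradiction inside one paragraph. The third row puts 6.2.1 at odds with both other sections, and the fourth with 2.1. Only the second row is consistent throughout.

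**Step 2: comparison with lipid drugs.** The treatment attribute in 2.1 names anti-diabetic and lipid-lowering medication together. Section 6.2.1 carries out the lipid half by allowing prescription to local standard of care. For anti-diabetics it gives no matching permission beyond the insulin sentence.

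**Step 3: the primary analysis.**

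- Addition or removal is ignored under treatment policy in 2.1 and 12.4.3, so an observed Week 48 biopsy counts. Section 12.4.4 imputes any primary endpoint after an intercurrent event, so the same biopsy would be replaced. The title of 12.4.4 refers to missing values not related to intercurrent events, but its text goes beyond that title.
- A dose change that is neither an addition nor a removal is not named in intercurrent event 3, although the treatment attribute in 2.1 does name it.
- The supplied SAP does not settle this. Its document history is dated December 2019 and it describes three arms without placebo. Its Section 2.5 uses a mix of while-on-treatment and hypothetical strategies, and its Section 2.5.3 contains the same imputation sentence as protocol 12.4.4. That sentence suits the SAP's hypothetical strategy, but not the treatment policy the current protocol sets for this event.

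**The case against.** The case for leaving the text alone has substance.

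- **Hypoglycemia wording.** Section 10.2.3.5 is permissive. A change of 25% or less, or an interruption of study treatment, satisfies it and 6.2.1 together, and an insulin change does so if the insulin sentence is read as an exception. It never requires a larger change or a new agent. This stands: the two sections are unreconciled, but they are not in direct conflict in every case.
- **Insulin.** The specific sentence can be read as an exception to the general one. That is a fair reading, but Table 6-2 repeats the 25% condition for insulin without any exception.
- **Safety routes.** Section 6.2.1 sends doubtful cases to the sponsor's medical monitor. Section 14.1 expects immediate safety action even when it is a deviation. Exclusion criterion 7c removes participants on insulin or sulfonylureas whose HbA1c is below 6.5%. A reader might infer that participants would go untreated; given these provisions, the documents do not support that.
- **Intercurrent-event list.** Listing an event does not permit it. The same item in 12.4 covers prohibited medication and excess alcohol, alongside lipid drugs that 6.2.1 allows. A treatment-policy analysis can also use data after disallowed changes. This stands, so the conflict with the estimand rests on the medical-need wording of the treatment attribute in 2.1, not on the list.
- **Design choice.** Restricting new metabolic agents limits confounding of the histology and weight endpoints. The sponsor may choose that, but then the treatment attribute in 2.1 should say so.

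**Conclusion.** The inconsistency is real and should be fixed, as a matter of clarification rather than demonstrated harm. Section 6.2.1 with Table 6-2 contradicts itself on insulin. For oral anti-diabetics and GLP-1 agonists, its limit does not fit the treatment attribute of either primary estimand and is not reconciled with 10.2.3.5. A response the protocol itself foresees can be at once part of the treatment strategy and a deviation, and the primary analysis has two incompatible instructions for endpoints after added or removed medication.

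The number of participants affected cannot be derived. The documents give no expected share with T2DM, no share on each drug class and no rate of confirmed glucose below 56 mg/dL. A reader might infer that interruptions for hypoglycemia would lower exposure mainly in the two licogliflozin arms. Without event rates that is conjecture, and the conclusion does not depend on it. It rests only on the wording of the sections cited. No view is taken on which clinical rule is right.

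**What to change.** 1. Reconcile 2.1, 6.2.1, Table 6-2 and 10.2.3.5. State whether the post-entry limit on new use and on changes above 25% applies to changes made for safety or medical need, and make the insulin sentence and Table 6-2 agree. The clinical rule is for the sponsor to decide. Whatever is chosen, the treatment attribute in 2.1 and the definition of a protocol deviation should follow from it.
2. In 2.1 and 12.4.3, extend intercurrent event 3 to name dose changes as well as addition or removal, and align the list in 12.4 with it.
3. In 12.4.4, state that endpoints observed after this event are used as observed in the primary analysis, in line with treatment policy, and that imputation after the event belongs only to the hypothetical supplementary analysis. Carry the same rule into the SAP.

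The cost is a few sentences in the protocol and the matching SAP text. No new data are needed, because Sections 6.2.1 and 8.2.6 already require concomitant medication and its changes to be recorded. Using observed endpoints leaves variation in background therapy within the primary estimate. Treatment policy accepts that, and the supplementary analysis is there to examine it.
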